

Study Design

This is a prospective observational study. We will study patients undergoing major surgery, specifically Whipple procedures (pancreatico-duodenectomies) and compare AxV-128/Tc SPECT-CT scans before and after surgery in COPD and non-COPD patients.

Statistical Procedures

Serum biomarkers of inflammation and levels of apoptotic endothelial microparticles will be correlated with % injected dose of radiotracer on SPECT-CT imaging results. We will compare as primary endpoint apoptotic endothelial microparticles and serum biomarkers of inflammation pre- and post-operatively on patients undergoing Whipple operations or other major surgery. If we assume that a correlation coefficient of 0.7 is clinically relevant we will require 15 subjects to achieve a power $(1 - \beta) = 0.8$ with a Type I error $(\alpha) = 0.025$. We will recruit 40 subjects total, 20 subjects with COPD and 20 subjects without COPD.

Confidentiality and Privacy

All subject identifiers will be removed after collection of the data and the data will receive a code that will allow us to link this data to the medical record number using a linking code. The linking code will be stored on a locked and secured, encrypted computer of the principal or the investigators. Access to any of the data will be restricted to the principal investigator and the coinvestigators by assignment of a password. The computers storing the data will be stored in a locked up room and will only be accessible to the principal investigator or the coinvestigators. Hard copies of research data such as data collection sheets will also be secured in a locked up room and destroyed at the end of the study. Patient identifiers (including but not restricted to names or Medical record numbers) will be removed once the data have been entered into a computer database. Access to this data will be restricted by assignment of password. Computers that contain these data will be securely locked up to prevent access by unauthorized people.

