Patient identifiers (including but not restricted to names or Medical record numbers) will be removed once the data have been entered into a computer database. Access to this database will be restricted by assignment of password. Computers that contain this data will be securely locked up to protect privacy, and to prevent access by unauthorized users. Discussions about research participation will take place in the privacy of the patient's hospital room. Limitations to protection include the disclosure of research notes and mandatory reporting.

Study Procedures

We will study patients undergoing major surgery (e.g., Whipple procedures (pancreatico-duodenectomies), biliary reconstruction or partial hepatectomy) and compare AxV-128/Tc SPECT-CT scans before and after surgery in COPD and non-COPD patients. These procedures such as the Whipple procedure have been chosen because the surgery itself is unlikely to injure the lung, but is a surgery with long enough duration of mechanical ventilation to potentially induce lung injury (80). Other major surgeries may be studied as well. Twenty patients with moderate COPD (Gold stage II: FEV1/FVC<0.70 and FEV1 50-79% normal) and twenty patients with normal lung function undergoing Whipple procedures or other major surgeries will be enrolled in the study. After obtaining informed consent the subjects will undergo spirometry for baseline lung function testing. The subjects will then undergo a baseline AxV-128/Tc SPECT-CT scan at least 2 days prior to surgery. The peri-operative management including the intra-operative ventilatory and anesthetic management will be left to the discretion of the clinical care team. Two to three days after surgery, patients will undergo repeat AxV-128/Tc SPECT-CT scan.

At each scan a blood sample to correlate serum biomarkers and a urine sample to measure cotinine to confirm the smoking status of the subject will be drawn. For the post-operative imaging, we will exclude patients with hemodynamic instability (vasopressor requirement at 36 hours post-operatively), inability to transport due to other clinical instability as determined by clinical care team or withdrawal of consent. Blood samples will be also stored for possible future DNA and RNA analysis.

Pulmonary Function Testing:

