Mean \pm SD for values for uptake of AxV-128/Tc for individual lobes and for lungs will be determined for each COPD group and compared using unpaired t-test for values with Gaussian distribution and Mann-Whitney (Wilcoxon rank) test for continuous variables without normal distribution. Gaussian distribution will be determined using the Kolmogorov-Smirnov test. We have included moderate, severe and very severe COPD patients assuming that the signal will increase with the severity of COPD. We could therefore establish an exposure-response relationship between severity of COPD (on a non-linear scale) and signal. This assumption is based upon our work establishing a correlation between COPD severity and apoptotic index in the lung (12). Mean \pm SD for values for volumes and Hounsfield units will also be compared among the same groups. We will also assess tracer uptake normalized for lung volumes. In the emphysema patients we are measuring a signal coming from living (and dying) tissue that is interspersed in air. In the more severe cases of COPD, the lung tissue takes up less volume within the lungs and the air forms greater percent of each lobe. We will attempt to account for these changes by normalization for Hounsfield units. In addition values for %ID tracer uptake will be correlated with values for PA:A ratio. For the serial reproducibility studies, the values for whole lungs and lobes from the two studies will be analyzed for agreement using Bland-Altman analysis.

Study drug

Name: Tc-99m rhAnnexin V-128

Dose: 10 mCi

Study phase: Phase 2

Manufacturer Information: Advanced Accelerator Applications, USA

Route of administration: Intravenous

Recruitment/Screening Procedures

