All patients scheduled to undergo Whipple surgery or other major surgeries at Columbia University Medical Center (CUMC) will be eligible for enrollment. Eligible patients will be identified and approached by the surgeon or anesthesiologist in charge of their care to ask if they are willing to discuss participation in this study. Flyers will also be placed in waiting room of pancreatic clinic. If the patient agrees to discuss participation, a member of the research team will contact the patient, explain the study including risks and benefits in order to obtain informed consent preoperatively. Patients will be consented in their respective hospital room. The consent will not be sought on the same day of the patient's surgery. At a minimum, the surgeon will provide the consent form to the patient prior to the day of surgery. If participant continues to express interest after the study was thoroughly explained, we then inquire if it is OK to proceed with eligibility questions. We go over the inclusion and exclusion criteria as listed below:

Eligibility Questions: Inclusion Questions: (I) Males and females age 45-80 years (II) Able and willing to comply with the study procedures (III) Will undergo major surgical procedure (IV) Non-Smoker (V) Lie flat for 30 minutes? Exclusion Questions: (I) Current Lung Malignancy (II) Recent COPD exacerbation (less than 1 month) (III) Recent pulmonary infection (less than 1 month) (IV) Asthma or other significant lung disease (V) Pregnancy or lactation (VI) Have high creatinine level (VII) Have smoked within the last 30 days (any type of smoking – cigarettes, marijuana...etc.)

As part of the screening, subjects will self-report their medical history over the phone to the study team (i.e., smoking history, COPD Exacerbation history, medications and medical history relevant to study and Alpha-1 deficient or carrier state if applicable). For subjects whom can provide medical records, these will not be accessed until the subject has signed the informed consent form. Please note that the eligibility screener form serves as the source document for patient's self-reported medical history.

After Screening Procedures:

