If they seem to meet the criteria, we then ask if it is OK to maintain their contact information (including: name, phone number, address and DOB) to give them a call back once an investigator has agreed upon their eligibility status to participate in the study (and signed the eligibility/screener internal document). Please note, the investigator, CRC and surgical clinical staff have pre-screened the potential participant and provided access for the CRC to introduce study after clinic appointment with surgeon. After thoroughly explaining the study and verifying eligibility, the participant may be consented and study procedures may be scheduled for prior and after to the surgery date.

Research Question(s)/Hypothesis(es)

Investigate the hypothesis that AxV-128/Tc SPECT-CT imaging identifies peri-operative lung injury-
Investigate the hypothesis that AxV-128/Tc SPECT-CT imaging discerns more severe perioperative lung injury in patients with COPD compared to patients without COPD.

Scientific Abstract

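### The COPD versus non-COPD uptake comparison is unadjusted and unmatched, so a group difference in age, and possibly in past smoking, can be mistaken for a COPD difference

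*Combined protocol and SAP*

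**What the plan says.** - **Design.** The Study Design section states: "This is a prospective observational study". Group membership is a patient characteristic, not an assignment.
- **Groups.** Statistical Procedures: "We will recruit 40 subjects total, 20 subjects with COPD and 20 subjects without COPD". Study Procedures defines the COPD group as moderate disease and the comparison group as "twenty patients with normal lung function undergoing Whipple procedures or other major surgeries will be enrolled in the study". Neither section mentions matching or stratified recruitment.
- **Test.** Imaging and data analysis has uptake by lobe and for the lungs "compared using unpaired t-test for values with Gaussian distribution and Mann-Whitney (Wilcoxon rank) test for continuous variables without normal distribution". No covariate is named. The section does not say whether baseline uptake, post-operative uptake or the change is tested.
- **Adjustments described.** "We will also assess tracer uptake normalized for lung volumes", and normalisation for Hounsfield units. Both concern how much tissue lies in the imaged volume.
- **Hypothesis served.** The second research hypothesis is that imaging "discerns more severe perioperative lung injury in patients with COPD compared to patients without COPD". No other between-group test is named for it.
- **Patient factors.** Under Recruitment/Screening Procedures the age criterion is "Males and females age 45-80 years", smoking in the previous 30 days excludes a patient, and self-report at screening covers "smoking history, COPD Exacerbation history, medications and medical history relevant to study". Urine cotinine is measured at each scan.
- **Interpretation.** Imaging and data analysis also says that an exposure-response relationship between COPD severity and signal could be established.

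**The concern.** A two-group test between patients who differ in disease status also picks up whatever else differs between them. Two factors are plausible from the documents themselves.

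- **Past smoking.** The Study Purpose and Rationale names tobacco smoke as a trigger of COPD, so more ex-smokers are to be expected in the COPD group. The Scientific Abstract says that apoptosis imaging has shown smoke-inhalation lung injury in animals, so smoke exposure might bear on uptake too.
- **Age.** Eligibility spans 35 years and nothing balances age between the groups.

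The safeguards present do not cover this. The 30-day exclusion and cotinine deal with recent smoking, not cumulative exposure. Normalisation for lung volume and Hounsfield units deals with tissue density.

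The second hypothesis is at stake. A positive test might reflect age or smoke exposure rather than COPD, and an imbalance in the other direction could hide a real difference.

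**Working it through.** **The plan's only sample-size figure.** It concerns the correlation between biomarkers and uptake: 15 subjects for r = 0.7, power 0.8, alpha 0.025. By Fisher's z, n = ((z_alpha + z_power)/atanh(0.7))² + 3. With two-sided alpha 0.025 this is ((2.241 + 0.842)/0.867)² + 3 = 15.6, so 16, or 15 with the small-sample bias correction. The figure reproduces, but it says nothing about the group comparison, for which no power is given. A two-sided 5% t-test at 20 versus 20 has 80% power for a difference of about 0.91 SD.

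**Inputs for the check.** From the documents: 20 per group and an unpaired test. Assumed, because the documents do not give them: two-sided alpha 0.05, no true COPD effect, the age gap, a within-group age SD of 9 years, and the correlation r between age and the uptake measure tested.

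**Formulas.** Shift in SD units: b = r × (age gap)/9. The unadjusted t statistic then has 38 degrees of freedom and noncentrality b/√(2/20) = 3.162 × b.

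| Assumption | b (SD) | Noncentrality | False-positive rate |
|---|---|---|---|
| No imbalance, or r = 0 | 0 | 0 | 5.0% |
| Gap 4 years, r = 0.2 | 0.089 | 0.28 | 5.9% |
| Gap 8 years, r = 0.3 | 0.267 | 0.84 | 13.0% |
| Gap 10 years, r = 0.4 | 0.444 | 1.41 | 27.8% |
| Total shift of 0.5 SD | 0.500 | 1.58 | 33.8% |

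For smoking alone, suppose all COPD patients but half of controls are ex-smokers and smoking moves uptake by 0.5 SD. The shift is 0.5 × 0.5 = 0.25 SD and the rate is 12.0%. Adding the 8-year age case gives 0.267 + 0.25 = 0.517 SD, just above the last row.

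**Cost of adjusting for age.** For a gap of D = 8/9 = 0.89 SD, the variance inflation of the group term is 1 + D²/4 = 1.20. Age removes r² = 0.09 of the residual variance. The standard error ratio is √(0.91 × 1.1975) = 1.04, or 1.06 with the factor 38/37 for the lost degree of freedom.

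**Cost of adding smoking.** In the scenario above, the pooled within-group variance of ever-smoking is (0 + 0.25)/2 = 0.125. Smoking alone gives an inflation of 1 + (0.5²/0.125)/4 = 1.50. With age the total is 1 + 0.50 + 0.20 = 1.70. The residual variance is 1 − 0.09 − 0.5² × 0.125 = 0.88. The ratio is √(1.70 × 0.88) = 1.22, or 1.25 with the factor 38/36. Simulation gives 1.24. The detectable difference rises from 0.91 to about 0.91 × 1.24 = 1.13 SD.

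**The case against.** **The hypothesis may be descriptive.** It can be read as asking only whether the scan separates two kinds of patient, and an unadjusted comparison answers that. This stands, and it is why the planned test should stay. It does not cover the exposure-response sentence, which goes beyond description. That sentence also sits in text describing moderate, severe and very severe COPD, whereas Study Procedures enrols moderate COPD only. The two sections must be reconciled.

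**Smoking is upstream of COPD.** Adjusting for it asks about COPD beyond its smoke exposure, which no hypothesis poses. A past exposure that affects uptake by its own route would still confound, but the documents do not show that it does: the animal evidence concerns smoke inhalation, not remote smoking in people. The objection stands against making the smoking-adjusted difference the answer to the second hypothesis, but not against a sensitivity analysis.

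**Change scores would cancel stable differences.** If pre-to-post change is tested, lasting age or smoking effects on uptake largely drop out, and only differences in the response to surgery remain. This is correct, and r in the table would then be the correlation with change. The plan does not say that change is tested.

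**Every magnitude is assumed.** This also stands. The low end, 6% against 5%, is negligible.

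**Conclusion.** The gap is real: the named test is unadjusted, the groups are neither randomised nor matched, and no other provision addresses age or past smoking. The conclusion is that a COPD difference can be confused with an age difference, and possibly with a past-smoking difference.

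A reader might infer more: that such differences will be reported as an effect of COPD. The documents do not support that. They contain no data showing that the groups differ in age or past smoking, or that either affects uptake, and the hypothesis does not require a causal report.

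The size is therefore unknown. The false-positive rate stays at 5% without imbalance or association, is 6% to 28% over the assumed age range, and is 34% at a 0.5 SD shift. These figures assume a two-sided 5% t-test, no true COPD effect and a linear age effect. The remedy is cheap enough to be worth making.

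**What to change.** 1. Keep the unpaired t-test or Mann-Whitney test as the description of the two groups, and name the uptake measure it uses.
2. Pre-specify beside it a linear model of pre-to-post uptake change (log scale if skewed) on COPD group with age as covariate. Report the adjusted difference with its 95% CI.
3. State that a difference will not be attributed to COPD itself unless it persists in the adjusted model.
4. Tabulate age and smoking history by group.
5. Add smoking history (pack-years, or ever/never if pack-years are unknown) as a sensitivity analysis only.

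**Cost.** Analysis wording only. Age and self-reported smoking history are already collected, so no new visit or patient is needed; pack-years depend on how much detail the screener records. Age uses about 1 of 38 degrees of freedom and, under the assumed 8-year gap, enlarges the standard error by about 4% to 6%. The sensitivity model is dearer: about 24% larger if all COPD patients but half of controls are ex-smokers. In that case no COPD patient is a never-smoker, so the smoking-adjusted contrast in effect compares 20 COPD patients with 10 controls and otherwise relies on the model. Counting only the 2 degrees of freedom would understate this.
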